7.3.3.2. Disease Control Rate

Disease control rate is defined as the proportion of participants with an overall response (CR and PR) or SD at any postbaseline visit before first PD or new anticancer therapy. The DCR will be calculated, and exact 95% CI will be reported.

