8.6. Unscheduled Visits

Unscheduled study visits may occur at any time if medically warranted. Any assessments performed at those visits should be recorded in the eCRF.

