10.4.2.2. Disease Control Rate

Disease control rate is defined as the proportion of participants with either an objective response (CR or PR) or SD, according to RECIST v1.1.

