4.1.6. Cycle Length and Duration

One cycle is 28 days (4 weeks) for all participants in this study. Cycle 1 Day 1 is the day the first infusion of INCMGA00012, with the exception for records of clinical laboratory tests, vital signs, and ECGs, where visit Cycle 1 Day 1 could be within 7 days before the day of first infusion of INCMGA00012. Day 1 of subsequent cycles will correspond to the infusion date of INCMGA00012 within the cycle. Tumor assessments follow Protocol-defined schedule, that is, Q8W with \pm 7-day window within 1 year and Q12W with \pm 14-day window after 1 year. Analysis of tumor response assessments follow the same time window.

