7.3.2.2. Best Overall Response

The BOR is the best response recorded from the start of the treatment until the first PD, in the order of CR, PR, SD, PD, and NE. Responses of CR, PR, or SD after a response of PD will not be considered in determining best response. The BOR will be determined from response assessments before or on the same day as new anticancer therapy. If any alternative cancer therapy is taken while on study, any subsequent assessments will be excluded from the BOR determination. In the case of SD, measurements must meet the SD criteria at least after the date of first dose at a minimum of 7 weeks.

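### DCR in the SAP counts stable disease at any postbaseline visit, but BOR requires at least 7 weeks, so SD seen only on an early scan can raise DCR above CR+PR+SD in the BOR table

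*SAP*

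**What the plan says.** SAP 7.3.3.2 credits disease control for CR, PR "or SD at any postbaseline visit before first PD or new anticancer therapy". It sets no minimum time from first dose and does not refer to BOR. The rate is reported with an exact 95% CI.

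SAP 7.3.2.2 ranks best response "in the order of CR, PR, SD, PD, and NE", up to first PD, and adds: "In the case of SD, measurements must meet the SD criteria at least after the date of first dose at a minimum of 7 weeks".

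The protocol definition, in Section 10.4.2.2, also has no minimum: "Disease control rate is defined as the proportion of participants with either an objective response (CR or PR) or SD, according to RECIST v1.1". The endpoint tables in both documents (Protocol Section 3, SAP 2.2) read the same way.

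Three further passages bear on timing:

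- SAP 4.1.6: "Tumor assessments follow Protocol-defined schedule, that is, Q8W with" a window of 7 days either side in the first year. It continues: "Analysis of tumor response assessments follow the same time window".
- Protocol 8.6: "Unscheduled study visits may occur at any time if medically warranted". Assessments made at those visits go into the eCRF.
- SAP Table 4 treats PD found between scheduled assessments as a PFS event.

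SAP Appendix A lists a BOR summary table (2.1.1) and no separate DCR table. SAP 10.1 declares no departure from the protocol-defined analyses.

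**The concern.** DCR is a secondary endpoint, and a reader will normally expect it to equal the CR, PR and SD rows of the BOR table added together. Here the SD row has a 7-week floor and the SD part of DCR has none, and nothing in the SAP carries the floor across or says that the difference is intended.

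Two programmers following the SAP could report different DCRs from the same data, one from BOR categories and one from visit-level responses. The discrepancy from the 7-week rule runs one way: SD seen only before 7 weeks can add a participant to DCR and cannot remove one.

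**Working it through.** **Inputs.** Cohort size of about 30 (SAP 3.5); scans every 8 weeks with a 7-day window (SAP 4.1.6); SD minimum of 7 weeks for BOR (SAP 7.3.2.2) and none for DCR (SAP 7.3.3.2); exact 95% CI (SAP 7.3.3.2), two-sided (SAP 3.4).

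**1. The plan's own intervals.** No DCR figure is given, but SAP Table 2 gives 95% CIs for ORR at n = 30. The Clopper-Pearson limits are: lower = Beta quantile 0.025 with parameters (x, n − x + 1); upper = Beta quantile 0.975 with parameters (x + 1, n − x). For x = 3, 5, 7, 9, 11 and 12 they give 2.1–26.5, 5.6–34.7, 9.9–42.3, 14.7–49.4, 19.9–56.1 and 22.7–59.4. All six rows match.

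**2. Where the two SD rules part.** Counting from first dose, the earliest in-window first scan falls at 8 × 7 − 7 = 49 days. The BOR minimum is 7 × 7 = 49 days (study Day 50 under SAP 4.1.3). A first scan in the window therefore passes both rules. They differ only for SD seen less than 49 days after first dose, with no later CR, PR or qualifying SD before PD or new therapy.

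**3. Both rules applied to the same histories.**

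| History | BOR (7.3.2.2) | DCR (7.3.3.2) |
|---|---|---|
| SD at week 8 | SD | counted |
| SD at week 5, SD at week 8 | SD | counted |
| SD at week 5, PD at week 8 | not SD; PD by the stated order | counted |
| SD at week 5, no later evaluable scan | not SD; NE by the stated order | counted |
| PD at week 5 | PD | not counted |

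The fourth history can arise because Protocol 8.2 requires no further disease assessments after treatment stops.

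**4. Size.** Each participant with a history like the third or fourth adds 1/30 = 3.3 points; two add 2/30 = 6.7 points. In the table below, the 18 participants with BOR of CR, PR or SD and the numbers with early SD only are assumed.

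| Early SD only | DCR as written (exact 95% CI) | DCR from BOR (exact 95% CI) |
|---|---|---|
| 0 | 18/30 = 60.0% (40.6, 77.3) | 18/30 = 60.0% (40.6, 77.3) |
| 1 | 19/30 = 63.3% (43.9, 80.1) | same |
| 2 | 20/30 = 66.7% (47.2, 82.7) | same |
| 3 | 21/30 = 70.0% (50.6, 85.3) | same |

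With 15 or 21 in place of 18, two early-SD participants move DCR from 50.0% to 56.7%, or from 70.0% to 76.7%.

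**5. A second mismatch.** BOR uses assessments up to and including the day that new anticancer therapy starts; DCR uses only those before it. This one acts in the opposite direction: a participant whose only qualifying assessment is on that day enters BOR but not DCR.

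**The case against.** The strongest reply is SAP 4.1.6. If response analysis follows the visit window, a week-5 scan is not an analysed visit for DCR either. The 7-week minimum for BOR then merely restates the opening of the window at 49 days, and the conflict disappears. This reading is possible, but the sentence does not say that scans outside the window are dropped. Table 4 uses PD found between scheduled assessments, although that row concerns dating PD and not crediting SD. If early scans were already excluded, the BOR minimum would also have nothing to do. The ambiguity therefore remains.

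Several other points on that side stand:

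- The protocol's DCR has no minimum either, so SAP 7.3.3.2 agrees with it. Stating openly that DCR has no minimum would also settle the matter.
- Protocol 8.6 permits unscheduled visits but does not mention imaging, and Protocol 8.2 keeps scans on calendar days. The COVID-19 flexibility describes longer windows and delays, not earlier scans. Nothing in the documents says how often early scans will occur.
- One participant moves DCR by 3.3 points, while the interval for 18/30 is 77.3 − 40.6 = 36.7 points wide. There is no hypothesis test, and no decision rule in the documents rests on DCR.

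A reader might also infer that DCR is inflated by the participants who fail earliest. The documents do not support that: early PD is excluded under both rules, and there is no information on who would have an early scan read as SD.

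**Conclusion.** The two SD rules differ on their face, and the difference can only add participants to DCR. It is confined to SD seen solely on unscheduled or early out-of-window scans. The size is 3.3 points per affected participant in a cohort of 30; the number affected is unknown and may be zero. The conclusion assumes that SAP 4.1.6 does not remove early scans from the response analysis.

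Two stronger statements are tempting and should not be made. The first is that DCR will differ from the BOR table; it may differ, and with no early-SD-only participant this mismatch has no effect. The second is that the SAP itself assigns such participants a BOR of PD or NE. That follows from the stated order once SD is disallowed, but the SAP does not say it.

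ORR is unaffected by the 7-week rule. Severity is minor.

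**What to change.** In SAP 7.3.3.2, define DCR as the proportion of FAS participants whose BOR under Section 7.3.2.2 is CR, PR or SD, with SD subject to the 7-week minimum, reported with the exact 95% CI. In SAP 7.3.2.2, state which BOR category applies when SD is seen only before 7 weeks.

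This makes DCR agree with the BOR table and brings the new-therapy cut-off for DCR into line with that for BOR. ORR in Section 7.3.2.1 also stops before new therapy, so its cut-off should be checked at the same time. Because the protocol's DCR has no SD minimum, record the change in SAP 10.1.

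The cost is a few sentences and no new data. DCR may be slightly lower.

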7.3.3.3. Progression-Free Survival

Progression-free survival is defined as the time from the first dose of study drug to the date of the first PD according to RECIST v1.1 or death due to any cause. Progression-free survival will be analyzed by the Kaplan-Meier method, including estimated median with 95% CI and KaplanMeier estimated probabilities at several timepoints. If participants have no observed death or disease progression before data cutoff or new anticancer therapy, the participants will be treated as censored at their last adequate tumor assessment before data cutoff or new anticancer

therapy according to Table 4. Date of death will be determined using the Death Report, Survival Follow Up, and Subject Status eCRFs.

7.3.3.4. Overall Survival

Overall survival is defined as the time from first dose of study drug to the date of death due to any cause. Date of death will be determined using the Death Report, Survival Follow Up, and Subject Status eCRFs. Participants who are lost to follow-up or still alive at the time of analysis will be censored at the last known alive date. The last known alive date is defined as the later of the last study visit and the date the participant was last known alive from the Survival Follow-Up and Subject Status eCRFs or any datasets with data entry that could reflect participant status. Kaplan Meier curves, medians, and 95% CIs of the medians will be presented for OS.

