Protocol Title: A Phase 2 Study of INCMGA00012 (PD-1 Inhibitor) in Participants With Selected Solid Tumors (POD1UM-203)

Protocol Number: INCMGA 0012-203

Objectives and Endpoints:

Table 1 presents the primary objective and endpoint.

Table 1:Primary Objective and Endpoint

Objective	Endpoint
Primary	
To assess the efficacy of INCMGA00012 in terms of the ORR in tumor types of interest.	ORR, defined as the percentage of participants having a CR or PR, according to RECIST v1.1 as determined by the investigator.

Overall Design:

Table 2 presents the key study design elements. Further study details are presented after the table.

Study Phase	Phase 2	
Clinical Indication	Treatment-naive metastatic NSCLC with high PD-L1 expression (TPS \geq 50%) and no EGFR, ALK, or ROS activating genomic tumor aberrations.	
	Locally-advanced or metastatic UC in cisplatin ineligible patients whose tumors express PD-L1 (CPS \geq 10 of PD-L1).	
	Unresectable or metastatic melanoma.	
	Locally advanced or metastatic clear-cell RCC without prior systemic treatment.	
Population	Male and female participants at least 18 years of age.	
Number of Participants	Approximately 120 participants will be enrolled into disease-specific cohorts of approximately 30 participants per cohort.	
Study Design	This is a Phase 2, open-label, multiple group, multicenter study.	
Estimated Duration of Study Participation	The study consists of 3 periods: screening, study drug treatment, and follow-up. Participants have up to 28 days to complete screening. Treatment duration with study drug may last up to 2 years in the absence of disease progression, intolerable toxicity, death, withdrawal of consent, lost to follow-up, or premature discontinuation for any other reason. Participants completing treatment or prematurely discontinuing the study drug will be followed for survival until death, withdrawal of consent, or the end of the study, whichever occurs first. Survival follow-up is not required of participants who have discontinued active treatment after the primary efficacy analysis is completed.	
Coordinating Principal Investigator	MD, Hungary	

Table 2:Key Study Design Elements

Treatment Groups and Duration:

All eligible participants will receive INCMGA00012 at the RP2D of 500 mg IV Q4W. Treatment will be administered by IV infusion over 30 minutes on Day 1 of each 28-day cycle. Subsequent treatment cycles may be delayed due to toxicity for up to 12 weeks (see Section 6.5 and Table 10).

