A participant may receive up to 2 years of study drug in the absence of disease progression or unacceptable toxicity. Participants will be evaluated for AEs/SAEs for approximately 28 days after the last dose of study drug and will be followed for irAEs for approximately 90 days after the last dose of study drug or until the start of a new anticancer therapy, whichever occurs first. The 90-day visit may be conducted via phone call. Survival follow-up is not required of participants who have discontinued study drug once the primary efficacy analysis is completed. The primary efficacy analysis will be performed once all participants have been followed for at least 6 months from the start of treatment or have prematurely discontinued study treatment. Thereafter, participants will be treated with INCMGA00012 if they derive clinical benefit as per standard of care for the disease and local guidelines.

CONFIDENTIAL

The complete study-specific assessment schedule required for participants in this clinical study is presented in Table 3. The analytes to be evaluated in the safety laboratory analyses are found in Table 12. Details regarding the sample collection for PK analyses are defined in Table 4.

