10.4.2.4. Overall Survival

Overall survival is defined as the time from first dose of study drug to the date of death due to any cause. Kaplan-Meier estimate of OS will be provided, including median and its 95% CI. Participants still alive at time of analysis will be censored at the date last confirmed to be alive. Kaplan-Meier curves, medians, and 95% CIs of the medians will be presented.

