Rationale for change: Per Section 10.4.1.1, the primary efficacy analysis will be performed once all participants have been followed for at least 6 months from the start of treatment or discontinued prematurely. The last participant was enrolled in the study in APR 2020, and all participants have been followed for at least 6 months or discontinued. For this type of benchmark study, it is sufficient for the secondary endpoint of OS to be estimated from the available participant information from the start of study treatment to the time of efficacy analysis. Additional data from disease follow-up and survival follow-up are no longer required.

4. Section 1, Protocol Summary (Table 3: Schedule of Activities); Section 4.1 Overall Design; Section 4.2, Overall Study Duration; Section 7.1.2, Discontinuation Procedures; Section 8.3.1 Adverse Events; Section 8.8.1 Safety Follow-Up; Section 9.4, Reporting of Serious Adverse Events

Description of change: Provided clarification that all AEs and SAEs will be collected for 28 days after the last dose of study drug, whereas irAEs will be collected until 90 days after the last dose of study drug or until the start of a new anticancer therapy, whichever occurs first. A 90-day visit can be performed by phone.

Rationale for change: Unconfounded safety assessments will no longer be possible once a new therapy has begun, and delaying treatment with other anticancer therapies is not an option for participants with progressive cancer.

5. Section 1, Protocol Summary, Section 8.1.4 Distribution of Reminder Cards

Description of change: Added clarification that some procedures may be conducted by phone call, where appropriate, or as per institutional guidelines during the COVID-19 pandemic. Due to COVID-19 pandemic, some tests may be done outside the regularly scheduled visits or may be conducted at the next scheduled visit. Details may be found in the eCRF guidelines or study monitoring plan, as applicable.

Rationale for change: To provide flexibility with study visits for the safety of participants during the COVID-19 pandemic.

6. Section 1, Protocol Summary (Table 4: Pharmacokinetic Sample Collections);

Rationale for change:	Description of change:	
	Rationale for change:	

7. Section 4.2, Overall Study Duration

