1. INTRODUCTION

This study is a Phase 2, open-label, multicenter study designed to assess the clinical activity and safety of INCMGA00012 in participants with advanced solid tumors where the efficacy of PD-1 inhibitors has previously been established.

The purpose of this SAP is to provide details of the statistical analyses that have been outlined in the Protocol. The scope of this plan includes the interim and final analyses that are planned and will be executed by the Department of Biostatistics or designee. The analyses of PK and pharmacodynamics that will be executed by the Department of Clinical Pharmacokinetics and respectively, are not described in detail in this SAP.

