2. STUDY INFORMATION, OBJECTIVES, AND ENDPOINTS

2.1. Protocol and Case Report Form Version

This SAP is based on INCMGA 0012-203 Protocol Amendment 3 dated 10 DEC 2019 and CRFs approved 10 JAN 2019. Unless superseded by an amendment, this SAP will be effective for all subsequent Protocol amendments and CRF versions.

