3.2. Overall Study Duration

The study begins when the first participant signs the ICF. The end of the study is defined as the date of the last visit of the last participant in the study. Participants completing treatment or prematurely discontinuing the study drug will be followed for survival until death, withdrawal of consent, or the end of the study, whichever occurs first.

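### Does the undated censoring rule for overall survival bias OS once survival follow-up of off-drug participants stops?

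*SAP*

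**What the plan says.** Two protocol places limit survival follow-up. Table 2 of the Protocol Summary says "Survival follow-up is not required of participants who have discontinued active treatment after the primary efficacy analysis is completed", and section 4.1 says "Survival follow-up is not required of participants who have discontinued study drug once the primary efficacy analysis is completed".

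Neither OS analysis rule carries a date. Protocol 10.4.2.4 says "Participants still alive at time of analysis will be censored at the date last confirmed to be alive", and SAP 7.3.3.4 says "Participants who are lost to follow-up or still alive at the time of analysis will be censored at the last known alive date". The SAP lets the last known alive date come from any dataset that reflects participant status.

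The SAP describes follow-up differently. Section 3.2 says participants who complete or stop treatment "will be followed for survival until death, withdrawal of consent, or the end of the study, whichever occurs first", with no exception after the primary analysis. Section 2.1 adds that, unless an amendment supersedes it, "this SAP will be effective for all subsequent Protocol amendments and CRF versions".

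The protocol's intent for OS appears in the Amendment 4 rationale in Appendix C, which considers it sufficient for OS "to be estimated from the available participant information from the start of study treatment to the time of efficacy analysis".

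**The concern.** Read together, these rules appear to allow a biased estimate. After the primary analysis, a participant still on drug keeps generating visits, so the last known alive date keeps moving forward. A participant off drug has no required contact beyond the 28-day visit and the 90-day follow-up for immune-related events. In an OS analysis at study end, the late risk set would consist mainly of people still on drug, who probably do better. Censoring would then be related to prognosis, and the right-hand part of the curve, perhaps the median too, could read too high.

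The omission is also peculiar to OS. The rules for duration of response and PFS refer to a data cutoff, and Protocol 10.4.1.1 rules out recalculating ORR after the primary analysis. SAP 1 states "The scope of this plan includes the interim and final analyses that are planned", which could be taken to mean that a second, final OS run is coming.

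**Working it through.** The documents give no OS rate, median or event count, so there is no plan figure to reproduce. The check has a textual part and a simulation.

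**1. Which analyses have a date.** Protocol 4.1 and 10.4.1.1 time one efficacy analysis: when every participant has 6 months from treatment start or has stopped early. Protocol 4.2 fixes study end by safety follow-up for immune-related events: 24 months + 90/30.4375 months = 26.96, the stated 27 months. No efficacy output is tied to that date. Amendment 3 removed the interim analysis and the SAP is based on Amendment 3, so the scope sentence in SAP 1 is at least partly leftover wording and weak evidence of a later OS run.

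**2. Version dates.** The latest SAP is dated 23 JUN 2020. The follow-up change came with protocol Amendment 4 on 25 NOV 2020. The sentence in SAP 3.2 still stands in Protocol Table 2, immediately before the exception. SAP 3.2 lacks only that later addition, and it describes conduct rather than setting an analysis rule.

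**3. How long a later window could be.** Enrollment ended in April 2020. Adding 24 months and 90 days gives about July 2022, roughly 20 months after Amendment 4. A later run would therefore matter if one were made.

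**4. Simulation of both cases.**

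- From the protocol: drug for up to 24 months, contact for 90 days after stopping, study end 27 months after last entry, primary cutoff 6 months after last entry (the first half of the trigger).
- Assumed: uniform accrual over 9 to 15 months, median time to stopping drug 3 to 9 months, median survival after stopping 6 to 15 months, on-drug death hazard 0.005 to 0.01 per month.
- Six combinations, 200,000 participants each.
- Estimator: Kaplan-Meier, S(t) = product of (1 − d/n) over death times.
- Censoring time at the primary analysis: P = accrual + 6 − entry.
- Censoring time in a later run: the smaller of max(P, stop time + 3) and accrual + 27 − entry.

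One scenario (stop median 6 months, survival after stop 10 months, hazard 0.01, accrual 12 months):

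| OS estimate | Median (months) | S(12) | S(18) | S(24) |
|---|---|---|---|---|
| Truth | 17.3 | 0.660 | 0.479 | 0.338 |
| Cut at primary analysis | 17.2 | 0.660 | 0.475 | no data beyond 12 + 6 = 18 |
| Later run, no late deaths captured | 20.8 | 0.673 | 0.537 | 0.460 |
| Later run, half captured | 17.3 | 0.663 | 0.479 | 0.310 |
| Later run, all captured | 16.4 | 0.654 | 0.446 | 0.262 |

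Across the six scenarios, 12-month OS cut at the primary analysis is within 0.001 of truth. A later run with no late deaths captured overstates S(18) by 0.03 to 0.07 and S(24) by 0.09 to 0.12. With all late deaths captured, S(24) is 0.04 to 0.10 too low.

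A second simulation varied the off-drug to on-drug death hazard ratio, with true median OS of 12 or 18 months. The change in the later-run median was:

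- ratio 2 to 5, no late deaths captured: +0.1 to +6.3 months;
- ratio 1: 0.0;
- ratio 0.5: −0.2 to −1.3;
- ratio 2 to 5, half captured: −1.0 to +0.3.

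**5. Against sampling error.** With 30 participants and survival near 50%, the standard error is at least √(0.5 × 0.5/30) = 0.091, so the 95% half-width is 1.96 × 0.091 = 0.179. The possible shift of 0.03 to 0.07 at 18 months is well inside that.

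**The case for a change.** The strongest case for a change is that a plan should not depend on an amendment rationale. The OS sections are operative text and carry no cutoff, although response, duration of response and PFS are each tied down. The SAP claims to govern later amendments yet describes follow-up that no longer applies. Low capture of late deaths is plausible, because Protocol 9.4 does not oblige investigators to seek events after participation ends and requires notice only of deaths considered related. One sentence would close the gap at almost no cost.

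Most of the facts in this stand. The date is missing, SAP 3.2 is out of date, and a later OS run is not forbidden. What does not follow is that the plan as written yields a wrong result. The bias needs an analysis that neither document schedules. A difference between an amendment log and the current text is not itself a defect, and here the log shows which reading is meant. The added sentence would write down the window already intended and would not alter the OS estimate at the primary analysis.

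One limit applies to the reassurance. The trigger is also met by participants who stopped drug early, so a late enrollee could have under 6 months of survival follow-up. The simulation's 6-month minimum is therefore an assumption, and it should not be read as proof that the early curve is untouched in a later run.

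**Conclusion.** No change to the plan. Read with the only dated efficacy analysis and the Amendment 4 rationale, the time of analysis for OS is the primary analysis. Required survival follow-up runs up to that point for participants both on and off drug. OS cut there is essentially unbiased under the assumed hazards. It will be immature: in simulated cohorts of 30 under the tabulated scenario, the median was not reached in about 54% of trials. The Amendment 4 rationale accepts OS estimated on the data available at that time.

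The bias belongs to an unplanned re-run. Its size rests wholly on assumed hazards and death capture, and its sign can reverse. OS is secondary and descriptive, Protocol 10.3 and SAP 3.4 exclude hypothesis testing, and no decision rule uses it. The conclusion would change only if a study-end OS analysis were planned.
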